12.0 Study Timelines

12.1 Describe the anticipated duration of the study needed to enroll all study subjects.

Study enrollment is anticipated to take 2 years. If subject numbers have not been met at 2 years, but we continue to have consistent enrollment, the study period may be extended.

12.2 Describe the duration of an individual subject's participation in the study. Include length of study visits, and overall study follow-up time.

Study visits will occur over a 4-week period. Subjects will be seen for 4 visits the first week and then 2 visits a week for the remaining 3 weeks (total of 10 visits). The first visit will take approximately 2.5-3 hours and subsequent visits will be approximately 1.5 hours in duration. Subjects who fail to attend approximately 80% of the visits (miss more than 2 sessions) will be removed from the study and treatment will be stopped.

12.3 Describe the estimated duration for the investigators to complete this study (i.e. all data is collected and all analyses have been completed).

Approximately 3.5 to 4 years. 1-2 years for study enrollment, 1-year follow-up, and up to 6 months for analyses.

13.0 Research Setting

13.1 Describe all facilities/sites/locations where you will be screening and conducting research procedures. Include a description of the security and privacy of the facilities (e.g. locked facility, limited access, privacy barriers). Facility, department, and type of room are relevant. Do not abbreviate facility names.

Example: "A classroom setting in the New Academic Building equipped with a computer with relevant survey administration software", "The angiogram suite at University Hospital downtown campus", The Clinical Research Unit in the Institute for Human Performance."

Initial study screening will be conducted via telephone. Consent, initial data collection, and rTMS treatment will occur at the Motion Analysis Lab at the Institute of Human Performance. Rehabilitation sessions will be administered at the rehabilitation gym on the second floor of the Institute of Human Performance. During the 4-week treatment sessions, instruments will be completed electronically after the rehabilitation sessions on the second floor of the Institute of Human Performance. Measurements after the 4-week treatment sessions will be administered electronically.

13.2 For research procedures being conducted, for this study, external to Upstate (e.g., in schools, out-of-state, internationally, etc.) describe:

- Site-specific regulations or customs affecting the research
- The composition and involvement of any community advisory board
- Local scientific and ethical review structure outside the organization.
- Local issues affecting the research and rights of research subjects.

NOTE: This question is not referring to multi-center research. If this research is being conducted internationally, Supplemental Form E must be completed and uploaded.

N/A: This study is not conducted outside of Upstate.

14.0 Resources and Qualifications

14.1 The Principal Investigator (PI) must confirm, in consultation with Chair and Dean as applicable, that adequate resources are present to conduct and complete the study compliantly and safely. Specifically:

- The proposed subject population(s) are available in sufficient numbers to meet the study requirements
- Sufficient funds are available to conduct and complete the study compliantly and safely
- The PI and study team have sufficient time to conduct and complete the study compliantly and safely
- The PI has determined that the named study team is qualified to conduct the research compliantly and to monitor the safety and welfare of the enrolled research subjects effectively
- The PI ensures that the study team is fully aware of his/her involvement in this study and the details of the study protocol
- The PI ensures that the study teams will only be involved in research procedures for which they have been trained, and are currently certified and/or licensed, if required.

Confirmed

14.2 Describe the availability of medical or psychological resources that subjects might need as a result of anticipated consequences of the research, if applicable. (e.g, “on-call availability of a counselor or psychologist for a study that screens subjects for depression”

We do not anticipate any significant adverse events from our protocol. If psychological or medical adverse events requiring immediate medical attention occur, 911 will be called for medical management. For any non-emergency physical or psychological adverse events subjects will be referred to their primary care physician. For subjects who do not have a primary care physician they will be referred to an urgent care center or a hospital emergency room.

14.3 Describe your process to ensure that all study team members are updated on the progress of the research and the regulatory requirements (including enrolled subjects, unanticipated problems etc.)

All study members involved in treatment sessions will be trained on the protocol and emergency response plans by the PI.

15.0 Provisions to Protect the Privacy Interests of Subjects

15.1 Describe how you will protect subjects' privacy interests during the course of the research and any steps you will take to make the subject feel at ease.

NOTE: Privacy refers to an individual's desire/right to control access to or to place limits on whom they interact with or whom they provide personal information. Privacy applies to the person. Confidentiality refers to how data collected about individuals for the research will be protected by the researcher from release. Confidentiality applies to the data.

Examples of appropriate responses include: "participant only meets with a study coordinator in a private office setting where no one can overhear", or "the participant is reminded that they are free to refuse to answer any questions that they do not feel comfortable answering."

Data collection and treatment will be performed in a private research or clinical setting at the Institute of Human Performance on Upstate's campus. Subjects will have the right to refuse to answer any question that they do not feel comfortable answering.

16.0 Confidentiality

A. Confidentiality/Security of Study Data

Describe the local procedures for maintenance of security and confidentiality of **study data and any records that will be reviewed for data collection.**

16.1 Where and how will all data and records be stored? Include information about: password protection, encryption, physical controls, authorization of access, certificates of confidentiality, and separation of identifiers and data, as applicable. Include physical (e.g. paper) and electronic files.

Personal-identifying information will be collected using Upstate's REDCap system. Any downloaded personal-identifying information will be kept on the PIs password protected office PC, located in his locked private office in the New Academic Building. Any documents containing personal identifying information will be kept in a locked cabinet located in a secure room on campus (either the PIs office or in the Motion Analysis Lab). Once data collection is completed all personal-identifying information will be removed from the dataset by the PI. Only de-identified data will be shared with other research members or used for publication/dissemination.

16.2 How long will the data be stored?

When study activities are completed, the data will be archived in REDCap, and stored on the PI's password protected computer in his private office ([name]) for up to seven years.

16.3 Who will have access to the data?

Only study personnel included on this IRB application.

16.4 Who is responsible for receipt or transmission of the data?

The principal investigator will be responsible for receipt or transmission of the data.

16.5 How will the data be transported/transmitted?

Any physical paper documentation will be transported by study personal in sealed envelopes between testing/treatment areas and storage areas. Electronic data will be transmitted between study personnel using Upstate email or OneDrive/Dropbox sharing feature.

B. Confidentiality of Study Specimens

Describe the local procedures for maintenance of confidentiality of study specimens.

N/A: No specimens will be collected or analyzed in this research.

(Skip to Section 17.0)

16.6 Where and how will all specimens be stored? Include information about: physical controls, authorization of access, and labeling of specimens, as applicable.

N/A

16.7 *How long will the specimens be stored?*

N/A

16.8 *Who will have access to the specimens?*

N/A

16.9 *Who is responsible for receipt or transmission of the specimens?*

N/A

16.10 *How will the specimens be transported?*

N/A

17.0 Provisions to Monitor the Data to Ensure the Safety of Subjects

N/A: This study is not enrolling subjects OR is limited to records review procedures only OR is a minimal risk study

17.1 Describe the plan to evaluate the data periodically regarding both harms and benefits to determine whether subjects remain safe. The plan might include establishing a data safety monitoring committee and a plan for reporting data monitoring committee findings to the IRB and the sponsor.

Subjects will be directly monitored by study personnel during the rTMS and rehabilitation sessions. During rTMS it is expected that some subjects may experience mild headaches, local scalp discomfort, and muscle twitching. Subjects will be consistently monitored and stimulation intensity will be reduced if symptoms are not tolerated or if muscle twitch magnification occurs. During rehabilitation sessions, it is expected that some subjects may experience temporary exacerbation of their normal symptoms. The physical therapist delivering care will monitor subjects and adjust treatment intensity based on the subject's tolerance. Subjects can also request to stop participation in the study at any time for any reason. Study personnel will be in close communication and if the protocol is consistently poorly tolerated by subjects the study will be paused and the protocol will be reviewed and changed as needed.

17.2 Describe what data are reviewed, including safety data, untoward events, and efficacy data.

EMG data and visual observation will be used to assess muscle activation during rTMS. Subject report will be used during rTMS and rehabilitation to monitor response.

17.3 Describe any primary or secondary safety endpoints.

Muscle activity spreading beyond the stimulated area or increasing in magnitude despite lowering stimulation intensity. Unpleasant sensation associated with the interventions that is deemed intolerable or excessive by the subject or research personnel.

17.4 Describe how the safety information will be collected (e.g., with case report forms, at study visits, by telephone calls with participants)

Muscle activation will be recorded via EMG. At the end and beginning (other than the first session) of every rTMS and rehabilitation session subjects will be asked to report any adverse events. This will be recorded on REDCap as either “none” or, if present, the symptoms will be documented.

17.5 Describe the frequency of safety data collection, including when safety data collection starts.

Safety data will be collected at every treatment session. This will occur before (to assess response to previous sessions), during, and after each treatment session.

17.6 Describe who will review the safety data.

The primary investigator and any study personnel involved in treatment delivery. If these individuals have concerns, they will discuss the safety data with the entire research team.

17.7 Describe the frequency of review of cumulative safety data.

Normal and expected mild adverse events will be dealt with by the treating provider and reported to the PI, as they occur. All events requiring subjects to stop a treatment will be discussed with the entire research team. The study team will have meetings at least every 3 months to discuss any safety concerns.

17.8 Describe the statistical tests for analyzing the safety data to determine whether harm is occurring.

Not applicable. Safety data will be monitored onsite by investigators.

17.9 Describe any conditions that trigger an immediate suspension of the research.

A seizure occurring in one of the participants.

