4.0 Study Design

4.1 Describe and explain the study design (e.g. case-control, cross-sectional, experimental, interventional, longitudinal, and observational). Indicate if there is randomization, blinding, control group, etc. If randomizing, explain how this will be achieved. For studies that have a complex study design (i.e., multiple arms and treatments), include a schematic diagram.

This study will have a pilot phase and a randomized phase. The pilot phase will include 1-3 subjects who will receive real rTMS and rehabilitation. Subjects in the placebo controlled randomize phase will receive rehabilitation combined with either real or sham rTMS. Randomization will be performed in REDCap and be stratified by upper or lower extremity. Randomization will occur in blocks of 4 to ensure equal distribution. Patients and the physical therapists delivering rehabilitation will be blinded to group allocation (real/sham rTMS). The researcher administering the rTMS will not be blinded.

Changes included in protocol version 2:

- Addition of new advertisement document that will be handed out by clinicians to potential subjects.
- Addition of a pilot phase that will include 1-3 unrandomized subjects.
- Adjusted the subject numbers to reflect the pilot phase subjects.
- Added [name] to the study team.
- Created new informed consent document for the pilot phase.

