11.0 Research Methods & Procedures

Provide a detailed description of the methods and procedures that will be used to carry out the study. Include a summary of study visits and procedures (i.e., schedule of events table) in the space below or as an attachment.

Please make sure to include:

- Dosing of drugs and other details of study drug administration and study treatments
- A list and description of any experimental procedures
- A list and description all tests & procedures that would not be done if the subjects were not in the study
- An explanation how study participation differs from the standard of care
- Procedures being performed to monitor subjects for safety or to minimize risks

Interventions: 4 weeks

- Treatment will start (week 1) with 4 consecutive rTMS and 2 PT sessions (skipping weekends)
- Sessions will continue at 2 times a week for a total of 10 sessions
- Measurements will occur at:
 - The first visit (except GROC)
 - The last visit of each week
 - At 4 time points after the termination of the interventions-via e-mail survey
 - 4 weeks
 - 3 months
 - 6 months
 - 1 year

First Session:

- Screening (Budapest Criterion, and TMS screening)
- Informed consent- during the phone screening subjects will be given the opportunity to have informed consent documents sent to them via email. Subjects will be given time to read the documents and ask questions about the study before agreeing to participate.
- Randomization
- Baseline measurements
- rTMS/sham rTMS session
- PT session

Subsequent Sessions (9):

- TMS screening
- rTMS/sham rTMS (the first week 2/4 sessions will not include a PT session)
- PT session
- Repeat measurements will be taken at the end of each week (4 in total)

Test and measures: All outcome measures are self-reported and collected using REDCap.

- Primary
 - Numeric Pain Rating Scale (NPRS) (0-10): Average score for the week

- Secondary Measures

- Numeric Pain Rating Score (0-10): Worse and least pain intensity over past 24 hours
- NIH Patient-Reported Outcomes Measurement Information System (PROMIS): Pain interference, pain behavior, physical functioning, satisfaction with discretionary social activity, satisfaction with social roles, fatigue, depression, anxiety, and anger.
- Patient Global Impression of Change (GROC) (only measured at follow-up)- scale rated from 0 (not important) to 7 (a very great deal important).

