- Patient Global Impression of Change Impact (GROCI) (only measured at follow-up)- scale rated from 0 (not important) to 7 (a very great deal important).
- Patient Acceptable Symptom State (PASS): “Considering all the different ways your pain symptoms are affecting you, if you were to stay in this state for the next few months, do you consider that your current state is satisfactory?” (Yes/No)
- Grip Strength (Subjects with UE symptoms only)- Measured using a dynamometer bilaterally.
- Leg Press 1 Repetition Maximum Test (Subjects with LE symptoms only): The subject will perform 2 warm-up sets with light resistance. Weight will be increased with the goal of finding the 1 repetition maximum weight within 4 trials. A 2-minute rest period will be given between trials.
- Patient Specific Functional Scale: Goals are set by PT and subject. The patient rates their ability to complete the task described in to goal on a 0(unable to perform) to 10 (Able to perform activity at the same level as before injury or problem).
- Adverse events
- Participant disposition: Who was enrolled/reasons for exclusion, reason for dropout (if known)

Interventions:

- rTMS:

- rTMS will be delivered using a commercially available magnetic stimulator (Rapid², Magstim Inc., Eden Prairie, MN) with a figure-of-8 coil at 10 Hz. With subjects in a seated position, the coil will be positioned on the scalp, contralateral to the subject’s symptomatic side. Coil orientation will be optimized for stimulation of the abductor pollicis brevis.
- Targeting:

Subjects will wear a lycra cap so marks can be made to facilitate proper targeting. Single-pulse stimulations will be delivered over various locations of the contralateral primary motor cortex to identify the optimal location for stimulation of the target muscle. Motor evoked potentials (MEP) of the abductor pollicis brevis will be monitored using electromyography (EMG) (Motion Lab Systems Inc., Baton Rouge, LA). Once the optimal stimulation position is identified a mark will be made on the lycra cap. The motor threshold (MT) of the muscle will then be

identified by systematically adjusting the pulse intensity. The MT will be considered the lowest stimulation intensity at which 5 out of 10 MEPs have a peak-to-peak amplitude of at least 50 microvolts, measured using RMG of the abductor pollicis brevis.

○ Parameters:

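### Adverse events are collected by an open question from an unnamed asker, apparently the unblinded rTMS researcher at rTMS sessions, and 5.1 plans no by-arm summary

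*Combined protocol and SAP*

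**What the plan says.** - **Status of the outcome.** Section 11.0 places "Adverse events" in its list of secondary measures. The analysis list in 5.1 has no entry for them.
- **How they are collected.** Section 17.4 provides that, at the end and the beginning (other than the first session) of "every rTMS and rehabilitation session subjects will be asked to report any adverse events". The REDCap entry is either none or, "if present, the symptoms will be documented". Section 17.4 mentions no checklist, severity grade or fixed wording.
- **Who is blinded.** Under 4.1 subjects and physical therapists are blinded, but "The researcher administering the rTMS will not be blinded".
- **Visit structure.** There are ten visits with rTMS. In section 11.0, "the first week 2/4 sessions will not include a PT session".
- **Expected effects.** Section 17.1 names mild headache, local scalp discomfort and muscle twitching. Sections 17.2 and 17.4 add that muscle activation is followed by EMG.
- **Safety statistics.** On tests to determine whether harm is occurring, 17.8 answers: "Not applicable. Safety data will be monitored onsite by investigators".

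**The concern.** Headache and scalp discomfort exist in the data only if the subject mentions them, and how often subjects mention them depends on how they are asked. With an open question, a person who knows the arm can probe further, or write more down, for subjects on real stimulation without intending to. An excess of side effects in the real arm could then reflect the enquiry as well as the treatment.

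The trial is sham-controlled, so a reader will look for tolerability by arm, and adverse events are a declared secondary measure. With no summary specified in 5.1, the population, the unit of counting and the grouping of free-text entries would all be chosen after the data are seen.

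**Working it through.** The plan gives no figure for adverse events, so there is none to reproduce. The check is a count of enquiries and a comparison of sections.

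**1. Sessions (11.0 and 12.2).** rTMS: 4 in week 1 plus 2 in each of 3 further weeks, 4 + 6 = 10. Rehabilitation: two of the week 1 visits have none, so 10 − 2 = 8.

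**2. Enquiries per subject (17.4).** There is one at the end of every session and one at the start of every session but the first.
- rTMS: 10 ends + 9 starts = 19.
- Rehabilitation: 8 ends + 7 starts = 15.
- Share at rTMS sessions: 19 / (19 + 15) = 19/34 = 56%.
- If the exemption covers only the very first rTMS start, rehabilitation has 16 and the share is 19/35 = 54%.

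**3. Who asks.** Section 17.4 is in the passive voice and names nobody. Three facts point to the rTMS researcher at rTMS sessions:
- Section 13.1 places rTMS in the Motion Analysis Lab and rehabilitation in a separate gym, and the researcher giving rTMS is the only staff role described for the stimulation session.
- Two visits have no therapist at all.
- Section 17.7 leaves expected mild events to the treating provider.

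This is a strong inference, not a stated fact. By the same inference, the blinded therapist asks at rehabilitation sessions.

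**4. Which effects are exposed.** Headache and scalp discomfort rest on report alone. Twitching has an EMG record at the target hand muscle, while section 11.0 has other muscles watched by eye. Twitching is therefore less exposed, though not wholly protected.

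**5. What the blinded enquiries can do.** They can recover an event that was missed at an rTMS session in either arm. They cannot take out an event that extra probing in the real arm has already put on record. They therefore reduce a difference by arm but need not remove it.

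**6. Size, as illustration only.** The documents give no adverse-event rates, so these values are assumptions.
- Suppose the true rate is 30% in both arms, every event is recorded in the real arm and a fraction s in the sham arm. The spurious difference is 0.30 × (1 − s): 7.5 points at s = 0.75, 15 points at s = 0.50 and 22.5 points at s = 0.25.
- Two extra prompted reports in one arm move its rate by 2/n: 2/15 = 13 points at 15 per arm (assuming the 30 subjects in 2.1 are split equally), and 2/10 = 20 points at 10 per arm (the 20 completers).

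**7. Would a test help?** Two-sided Fisher power for true rates of 50% against 10% is 0.30 at 10 per arm and 0.54 at 15 per arm. A formal comparison would be weak, and a descriptive table is the right level.

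**The case against.** The strongest reply is that the plan never says the unblinded researcher asks. Section 11.0 states that "All outcome measures are self-reported and collected using REDCap", and adverse events are on the list that follows. Subjects are blinded, and blinded therapists' sessions account for 15 of the 34 enquiries, at 8 of 10 visits. Under 17.5 the enquiry before each session also covers the response to previous sessions, so effects of the two rTMS-only visits can surface later with a therapist. Section 11.1 lists adverse events among instruments to be uploaded, so a structured form may exist outside these documents. Open questioning is an accepted method, free text from about 30 subjects can be coded, and the aims in 1.1 make no tolerability claim.

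Much of this stands, and it is why the point is minor. Two parts do not settle the matter. The self-report sentence also introduces dynamometer grip strength, a leg-press maximum and participant disposition, so it cannot be read literally for every item, and 17.4 describes subjects being asked. The list in 11.1 also includes participant disposition, so it does not establish that an adverse-event form exists.

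A reader might also infer that 17.8 rules out any comparison of harms. It does not: the question there concerns tests used in monitoring, and the answer leaves by-arm reporting open. The gap is in 5.1. Nor does the absence of a test cause ascertainment bias; that risk comes from the way events are elicited.

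**Conclusion.** The point holds as a minor one. Adverse events are a secondary measure collected by an open question. The asker is not named and, at rTMS sessions, is apparently unblinded; no by-arm summary is specified. Just over half of the scheduled enquiries (19 of 34, or 19 of 35 on the other reading of the exemption) fall at those sessions. Differential reporting of headache and scalp discomfort is a real possibility, reduced but not removed by the blinded therapists' enquiries and, for twitching, by EMG.

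The tempting stronger statement, that the protocol assigns the question to the unblinded operator and so biases the result by a known amount, is not supported. The asker is inferred, 56% is a share of enquiries rather than a measure of bias, and the point figures in the working rest on assumed rates and arm sizes.

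**What to change.** - **17.4:** have subjects in both arms complete the same short REDCap form themselves at the start and end of each session, before speaking with the rTMS operator. It should cover the expected effects, their severity, and a free field for anything else. Immediate safety handling stays exactly as planned.
- **5.1:** add a descriptive table by arm of the number of subjects with each event, among all randomised subjects who received at least one session, with exact 95% confidence intervals and no formal test.

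The cost is one form and one table. The downside is that a checklist will record more minor events in both arms. One source of difference remains: section 11.0 has sham subjects told that they may feel little or nothing, which could itself lower their reporting. The form does not remove this, and the by-arm results should be read with it in mind.

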rTMS will be performed at the identified optimal location at 10Hz using an intensity that is 80% of the MT. Pulse trains will be delivered for 10 seconds, with a 30 second rest for 20 repetitions. This will result in a total of 2,000 pulses of magnetic stimulation.

○ Safety:

The most common side effects during stimulation are local discomfort and headaches. Subjects will be asked to inform the researcher if they are unable to tolerate the rTMS. If they cannot tolerate the stimulation the subjects will be given two options. The first option will be to reduce the stimulation intensity to a point that is tolerable. The second option will be to stop the stimulation. If they elect to stop the stimulation the subject can decide to end participation in the study or try another session at a subsequent date. Subjects will also be monitored for EMG activity at the abductor pollicis brevis and visual twitch response at other muscles. If this activity increases over the course of the stimulation the intensity will be reduced.

- Sham rTMS:

- Sham rTMS will be performed using the same coil and delivery device used in the real rTMS group. The sham group will start with the same localization procedure as the real rTMS group. The magnet will then be moved over the vertex of the skull and the intensity will be dropped to 5% of the maximal stimulation output or half of the treatment intensity (40% of MT) used in the real rTMS group, whichever is lower. Subjects in both groups will be told that after localization, the stimulation intensity will be lowered for the treatment. The sham group will be told that with this lower intensity they may experience minimal to no sensation from the stimulus. Allocation will be disclosed to all participants after the last data collection timepoint.

- Rehabilitation:

- Rehabilitation will consist of education, value-based goal setting, Graded Motor Imagery (GMI) (3 components described below), meditation, and graded activity. Subjects will complete activities at treatment sessions and be asked to perform certain treatment activities at home.

- Week 1: Pain education, functional value-based goal setting, laterality training (first component of GMI), one task for graded activity (task-based on patient goals)
 - Week 2: Continue week 1 activity, add graded motor imagery (second component of GMI), progress 1st graded activity, and initiate 2nd graded activity exercise.

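### Section 17.6 makes the blinded physical therapists reviewers of rTMS-session safety data that could let them infer allocation in some subjects

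*Combined protocol and SAP*

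**What the plan says.** Section 4.1 sets the blinding: "Patients and the physical therapists delivering rehabilitation will be blinded to group allocation (real/sham rTMS"). It continues: "The researcher administering the rTMS will not be blinded". The PI's status is not stated.

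Section 17.6 lists the safety reviewers as "The primary investigator and any study personnel involved in treatment delivery", and adds: "If these individuals have concerns, they will discuss the safety data with the entire research team".

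Section 17.2 describes what they review: "EMG data and visual observation will be used to assess muscle activation during rTMS", together with what subjects report during rTMS and rehabilitation. Section 17.3 makes muscle activity that spreads, or that grows even after intensity has been lowered, a safety endpoint.

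Section 17.7 separates two kinds of event. For mild ones: "Normal and expected mild adverse events will be dealt with by the treating provider and reported to the PI". For the rest: "All events requiring subjects to stop a treatment will be discussed with the entire research team".

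Section 11.0 describes the two stimulation conditions. Both begin with the same localization procedure. Real rTMS is then given at the motor hotspot at 80% of MT. For sham, the coil is moved to the vertex and the intensity is the lower of 5% of maximal output or 40% of MT. Sham subjects are told they may feel little or nothing.

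**The concern.** The therapists deliver treatment, so the reviewer rule in 17.6 covers them as written. It gives them records from a procedure that differs between the arms in coil position, intensity and expected sensation, although 4.1 says they are not to know the arm.

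What is at stake is the sham control. The therapists adjust rehabilitation to tolerance (17.1, 19.3) and set the Patient Specific Functional Scale goals with the subject (11.0). The outcome instruments are completed after rehabilitation sessions during the treatment period (13.1). A therapist who infers the arm could progress or encourage subjects differently, or pass on an expectation. The primary NPRS is self-reported, so any bias would act through the subject.

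**Working it through.** No figure in the plan bears on this point, so the check compares the sections and then illustrates the size with assumed rates.

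**1. Does the reviewer rule include the therapists?** 17.1 describes the physical therapist as delivering care. 17.6 covers everyone involved in delivering treatment and makes no exception. Read literally, it includes them.

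**2. Does any section withhold rTMS-session data from them?**
- 16.1 requires de-identification before data are shared. That removes identity, not stimulation records.
- 16.3 gives access to all personnel on the IRB application, without limits by role.
- 17.1 says study personnel will be in close communication.
- 17.4 (adverse events) and 28.2 (device use) place records in REDCap, with no statement of user rights.

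No section provides masked summaries or a separate unblinded safety reviewer.

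**3. Which data could point to the arm?** Localization EMG exists in both arms and says nothing. EMG spread, twitch growth or an intensity reduction during the treatment trains is more plausible at the hotspot at 80% of MT than at the vertex at 40% of MT or less.

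**4. How informative would one event be?** Assume 1:1 allocation, as balanced blocks imply. By Bayes' rule,

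P(real | event) = p_real / (p_real + p_sham),

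where p is the proportion of subjects in each arm with an event that stops stimulation or reduces its intensity. The documents give neither rate; those below are assumptions.

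| p_real | p_sham 0% | 1% | 2% | 5% | 10% |
|---|---|---|---|---|---|
| 5% | 1.00 | 0.83 | 0.71 | 0.50 | 0.33 |
| 10% | 1.00 | 0.91 | 0.83 | 0.67 | 0.50 |
| 20% | 1.00 | 0.95 | 0.91 | 0.80 | 0.67 |

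For example, 0.10 / (0.10 + 0.01) = 0.91. An event is strong evidence if such events are rare under sham, and no evidence if the rates are equal.

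**5. Spill-over within a block.** Blocks are of 4, within upper- or lower-extremity strata (4.1), so 2 of 4 are real. If one subject is known to be real, 1 of the other 3 is real. For someone who knows the block size and membership, the chance for another subject in that block falls from 1/2 to 1/3.

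**6. Occasions.** There are 10 rTMS sessions, and 2 of the 4 in week 1 have no PT, so there are 10 - 2 = 8 PT sessions. 17.4 asks about adverse events at the start of each session except the first, and the first session includes PT (11.0). That leaves 8 - 1 = 7 start-of-rehabilitation questions per subject. These are occasions to hear about symptoms, not disclosures, and 17.4 does not say who asks.

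**The case against.** A reader might infer that the safety process itself discloses allocation, or that any stopped or reduced session comes close to revealing the real arm. The documents do not support either reading. No section shares assignment in safety review. Real stimulation is below motor threshold, and 19.1 says so, so EMG during the trains should usually be quiet in both arms. Section 17.1 expects headache, scalp discomfort and twitching in some subjects without naming an arm, and makes an intensity reduction conditional. With no rates by arm, near-certainty cannot be claimed.

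Nor does all safety information reach everyone. Whole-team discussion under 17.6 depends on a reviewer having concerns. Mild events go to the treating provider and the PI, and for an rTMS event that provider is naturally the unblinded operator. The stopped-treatment sentence in 17.7 also covers rehabilitation, and stopping a rehabilitation session says little about the arm. Team membership is not listed. That the team includes the therapists is a reasonable reading, but 17.6 is the firmer ground.

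Exposure has limits too. Stimulation and rehabilitation take place in different rooms (13.1). Team meetings are required only every 3 months against 4 weeks of treatment, although the timing of stopped-treatment discussions is not stated. Subjects can describe what they felt to a therapist whatever 17.6 says.

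All of this narrows the point. One argument would remove it: that 17.6 means each provider reviews only their own modality. That may be the intention, but the text does not say so.

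**Conclusion.** The point holds as a conflict between 4.1 and 17.6. Followed as written, the plan gives blinded therapists a reviewing role over rTMS-session data that could allow them to infer allocation in some subjects. Section 17.7 adds a route when a stimulation session is stopped. This weakens the blinding; it does not show that the blinding fails.

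The number of subjects affected cannot be estimated from the documents. Under the assumed rates, one event moves the probability of the real arm from 0.50 to anywhere between 0.33 and 1.00, and most of the scenarios lie above 0.50. The conclusion rests on three assumptions: that 17.6 is read literally, that events during the treatment trains are commoner under real stimulation, and, for the 17.7 route, that the entire research team includes the therapists. It should be corrected, because the correction is cheap and the trial's comparison depends on the sham control.

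**What to change.** Reconcile 17.6 and 17.7 with 4.1:

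1. Limit EMG, intensity changes, tolerance and stopped-stimulation records from rTMS sessions to the unblinded operator and the PI. If the PI delivers rehabilitation, which the documents do not say, use another existing team member who does not. Enforce this through REDCap user rights.
2. Have stopped stimulation sessions discussed by those reviewers. Therapists continue to record and review rehabilitation events.
3. Give therapists arm-neutral information, plus anything needed for a subject's immediate safety.
4. Log every instance in which a therapist is unblinded, with the reason.

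The cost is protocol wording and REDCap settings. No new post is needed, provided that an existing team member outside rehabilitation can act as reviewer. The downside is small: therapists see less stimulation detail, with the safety override retained. The change does not stop subjects from describing their sensations to therapists, so that route remains open.
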